A retrospective cohort data linkage study of patients aged 18 years and above registered in English general practices. This protocol is written following RECORD guidance [12].

Settings Describe the setting, locations, and relevant dates, including periods of recruitment, exposure, follow-up, and data collection.

1205 general practices in England contributing to the QResearch database, which is nationally representative. We defined cohorts during the COVID pandemic as between 24th January 2020 (the date of the first confirmed COVID-19 case in England) and study end (30th June 2021). We defined retrospective comparison cohorts as the 5 years prior to this date (24th January 2015- 23rd January 2020).

Data linkage

The study will include adult patients registered with the QResearch database. Practices must have been contributing to the QResearch database for at least 12 months. For the investigation of associations of pre-existing neuropsychological diseases and treatments (cohort 1) patients must be registered for at least a 12-month period before 24th January 2020. For the investigation of incidence of new neuropsychological diseases (cohort 2) patients must be registered for at least a 12-month period between January 2015 to 2020. The date of study entry is separately defined below for each study cohort.

Patients in QResearch will be linked to: (1) the ICNARC Case Mix Programme (CMP) database, the national clinical database from adult critical care; (2) the Hospital Episode Statistics (HES) data warehouse containing records of all patients admitted to NHS hospitals and Emergency departments in England; (3) the national registry of COVID-19 RT-PCR positive test results from Public Health England (PHE); and (4) Office of National Statistics COVID-19 mortality data, which includes all deaths due to COVID-19 in England. Data linkage will be based primarily on NHS number. For a description of the datasets see Supplemental material S1.

Participants

Give the eligibility criteria, and the sources and methods of selection of participants. Describe methods of follow-up. The methods of study population selection (such as codes or algorithms used to identify subjects) should be listed in detail.

Aim 1.

From the linked dataset, we will extract two cohorts to explore the association between neuropsychological diseases and treatments and hospitalisation, ICU admission or death:

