For cohort two, our primary outcome is the first occurrence of either hospital admission with SARI in the HES dataset (defined as a new ICD-10 code J09-J22 in the HES dataset) or ICU admission in the ICNARC CMP dataset with SARI (defined as any admission with unique diagnostic code any one of RE129 RE131 RE82 RE50 RE86 RE94 RE75 RE133 RE132 RE121 RE1 RE128 RE16 RE130 RE117 RE42 RE41) or death. Secondary outcomes will be each of these three events considered separately (I.e. SARI related hospital admission, ICU admission, death).

Aim 2.

Our primary outcome is development of new neuropsychological disease up to 1 year following hospital discharge which we define as having received a diagnostic code as below:

- Anxiety and stress-related disorders [ICD F40-48 and corresponding Read codes]
- Mood disorders [ICD F30-39 and corresponding Read codes]
- Psychotic disorders [ICD F20-29 and corresponding Read codes]
- Dementia [ICD F00-F03, G30, G31.0 ? and corresponding Read codes]

Secondary outcomes are the diagnosis of new neuropsychological disorders (as defined above) with treatment, and where numbers are available the new diagnosis with or without treatment of each class of disorders, each considered as a separate endpoint.

Neuropsychological treatments are defined as:

- Hypnotics and anxiolytics: (hypnotics, anxiolytics, barbiturates and methyprylone, benzodiazepines)
- Antidepressant drugs (Tricyclic and related antidepressant drugs, Monoamine-oxidase inhibitors, Selective serotonin re-uptake inhibitors, Other antidepressant drugs)
- Drugs used in psychoses and related disorders (Antipsychotic drugs and depot injections, Lithium salts, Phenothiazine derivatives)

Definition of exposures

Aim 1

Neuropsychological disease will be defined as an ordinal variable with the following three categories: no relevant diagnosis or drugs; diagnosis ever recorded without recent drug treatment; diagnosis present with recent drug treatment (with at least two prescriptions for neuropsychological treatments as above within the six months preceding study entry).

Our primary exposure is active neuropsychological disease on the study entry date which we define as having received a diagnostic code as above (24th January 2020 for cohort 1 and 24th January 2015 for cohort 2).

Aim 2.

The primary exposure is a hospital or ICU admission resulting from COVID-19 infection. Comparator exposures are hospital or ICU admission resulting from SARI.

Covariates

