- oral steroids

Intensive care stay (Aim 2)

- Length of stay
- Duration of advanced respiratory support (invasive ventilation)
- Use of sedation in the first 24 hours of admission

Effect Modifiers

For aim 1, we assessed these potential confounders by creating directed acyclic graphs (DAG) to determine which variables were likely to be to some extent caused by the presence of prior neuropsychological disorders (as the exposure of interest), and which were not likely to be caused by the presence of prior neuropsychological disorders, but were thought to be independently potential predictors of severe Covid outcomes.

Variables from the above list to be included in the model are all those grouped under: demographics; co-morbidities; lifestyle factors; plus prescription of any immunosuppressants and/or anticoagulants. Other medications (as these are not believed to affect the risk of severe Covid outcomes), and in-hospital factors (length of stay and use of sedation during intensive care admission, as these are outcomes potentially caused by Covid severity) will not be adjusted for.

For aim 2, our exposure of interest is admission to intensive care with SARI (compared to admission to intensive care with SARI. This exposure occurs at a fixed time which is used as the baseline for our time to event analysis in predicting the outcome of interest, and all other variables listed above are measured before this baseline. Therefore (depending on the available sample size and number of events), all the previously listed covariates of interest may be included in our adjusted models.

Data sources

Intensive Care Unit admission data will come from the ICNARC CMP dataset Hospital admission and mortality will come from the HES dataset

All exposures and confounders and neuropsychological outcomes will come from the QResearch database.

COVID-19 infection test status will come from the national registry of COVID-19 RT-PCR positive test results from Public Health England (PHE).

Bias

To limit the possible impact of COVID-19 testing bias (collider bias) we will analyse the entire QResearch eligible population, rather than restricting analysis to only those with a positive COVID-19 test.

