For aim 1, the various different neuropsychological conditions of patients in cohort 1 are likely to result in varying levels of exposure to covid-19, compared to the populations without these conditions, with some conditions likely to have a protective effect, but in other conditions the reverse is expected. We have added a secondary analysis to examine the effect of specific conditions in order to evaluate this.

For aim 2, the two cohorts have experienced their exposure of interest (ICU admission with either COVID or SARI) during different time frames. Patients with SARI (admitted to ICU between 2015 to 2020) will have longer follow-up, but patients with COVID (admitted to ICU during 2020/21) may have benefited from the recently increasing public awareness of mental health conditions. To combat this, we have capped all follow-up at a maximum of 1 year post ICU discharge, and we will include a time-dependent covariate to assess whether risk varies with time post discharge. We have also included a cohort of patients with SARI admitted during 2020/21 for comparison with the COVID cohort during the same time frame.

We will derive the E-value to estimate the extent unmeasured confounding.

Study Size

For aim 1 we will use the entire QResearch database of approx. 8.3 million adult patients to maximise precision and minimise selection bias. We chose to use the last 5 years of ICNARC data for SARI comparisons to use recent data whilst having sufficient numbers for comparison taking into account the numbers from previous studies and after linkage [13, 14].

For aim 2, we will use all known ICU admissions from the ICNARC database for SARI and/or COVID who can be linked to the QResearch database. In cohort 3 the expected sample size is in the region of 11,000 admissions in total, for cohort 4 it is likely to be in the region of 7,000 admissions per year, and for cohort 5 around 3,500 patients.

Quantitative variables

Quantitative variables will be treated as continuous variables without categorisation. Descriptive summary statistics (mean and standard deviation, median interquartile range or number (%) as appropriate) will be used to present sociodemographic and clinical characteristics of patients with and without COVID-19 infection for those with and without neuropsychiatric conditions or treatments.

Statistical Methods

Aim 1.

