Cause-specific Royston Parmar flexible parametric models will be used to estimate the hazard ratios of developing new neuropsychological diseases after having received intensive care, comparing patients who received intensive care for COVID-19 (cohort 3) vs those who received intensive care for SARI (cohort 4). This model will adjust for all previously listed covariates. The age variable will be included as a restricted cubic spline rather than a linear term. Follow-up will start on the date of discharge from hospital.

Proportional hazards assumption will be tested, and time dependent terms will be included if the hazard ratio changes over time. A random frailty term will be included to account for similarities amongst patients admitted in the same critical care unit

A limited number of two-way interactions which are considered to be clinically or biologically plausible will be identified prior to analysis, and tested using a Wald test.

Primary care data on some potential confounding variables is incomplete (e.g. smoking status, alcohol intake, ethnic group, BMI). Reason for admission is mandatory for all records in the ICNARC database (the core dataset for aim 2), so classification of these reasons as either SARI or COVID related will be non-missing for all patients. Only admission records for completed critical care stay (non-missing length of stay and survival status at end of critical care) will be included (n.b. outcomes are missing in <1% of COVID ICU admissions to date). Remaining variables from the critical care stay are use of sedation in the first 24 hours, and duration of advanced respiratory support, which are missing for a small number of patients (<1.5%).

Both aims.

To allow data analysis with all eligible patients, we will impute missing data in all cohorts. We will use multiple imputation with chained equations under the missing at random assumption to replace missing values and use these values in our main analyses [15]. We will include all exposure and confounding variables in the imputation model, along with the Nelson–Aalen estimator of the baseline cumulative hazard, and the outcome indicator. We will carry out five imputations. Analysis models will be fitted in each imputed dataset and Rubin's rules to will be used to combine the results across the imputed datasets.

As the analyses are on time to event data, patients will be censored at the date when they are lost to follow-up as defined in cohort definitions above.

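### Aim 2 takes new neuropsychological disorders from the GP database alone, so linked hospital diagnoses are used neither to find a new disorder nor to show that it is new

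*Protocol*

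**What the plan says.** The Aim 2 primary outcome (Protocol, Variables, Aim 2) is "development of new neuropsychological disease up to 1 year following hospital discharge which we define as having received a diagnostic code as below". Each disease group is then given in two code systems, for example "Psychotic disorders [ICD F20-29 and corresponding Read codes". The dementia entry still carries an unresolved question mark: "Dementia [ICD F00-F03, G30, G31.0 ? and corresponding Read codes". That section does not name the dataset in which the codes are to be searched.

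The Data sources section does: "All exposures and confounders and neuropsychological outcomes will come from the QResearch database". HES is given a narrower role: "Hospital admission and mortality will come from the HES dataset".

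HES is nevertheless linked. The first Data linkage section describes it as "the Hospital Episode Statistics (HES) data warehouse containing records of all patients admitted to NHS hospitals and Emergency departments in England". The cohort 2 outcome is defined by new ICD-10 respiratory codes (J09-J22) in HES, so diagnosis codes will be extracted from it in any case.

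The stated Aim 2 model is fitted "comparing patients who received intensive care for COVID-19 (cohort 3) vs those who received intensive care for SARI (cohort 4". Cohort 5, SARI patients admitted during the pandemic, is defined under Participants and justified under Bias as a same-period comparator. It is not named in the Aim 2 model or in the sensitivity analyses.

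**The concern.** Aim 2 is about disorders that appear after a hospital stay, in patients who may be readmitted. If such a disorder is diagnosed at a readmission, the outcome depends on someone later entering a code in the GP record. If that happens late, the event date moves and may fall outside the one-year window. If it does not happen, the event is lost.

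The baseline has the matching gap. A disorder is new only if the earlier history is clear, and that history comes from the same single source. A patient whose earlier disorder was recorded only in hospital enters as disease-free, and a GP code after discharge then counts as incident. The Discussion criticises earlier ICU studies for not knowing patients' prior neuropsychological disease, so this matters to the study's own case.

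Objective 4 is an absolute incidence, and no comparator cohort corrects it. The hypothesis refers to severe outcomes, and the Sensitivity analyses section already expects low event rates for Aim 2. The two-code listing also leaves room for two analysts to build different primary outcomes, one from GP codes and one from both sources.

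**Working it through.** The Protocol gives no Aim 2 event rate, effect size or coding completeness, so there is no planned figure to reproduce. The check is a reading of the sections, followed by simple arithmetic under stated assumptions.

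**Sections side by side**

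| Item | What the Protocol fixes |
|---|---|
| Outcome code systems (Variables, Aim 2) | ICD ranges plus Read codes; dataset not named |
| Outcome source (Data sources) | QResearch only |
| Role of HES (Data sources) | Admissions and mortality |
| HES diagnosis codes used elsewhere (Variables, cohort 2) | Yes, ICD-10 J09-J22 |
| HES diagnoses used for new disorders or prior history | None, including in Sensitivity analyses |

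**Effect on incidence.** Let *c* be the share of new disorders recorded in either source that reach the GP record within the year. Then

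GP-only incidence ≈ *c* × incidence from either source.

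Input from Study Size: cohort 3 is about 11,000 admissions. Assumptions, not in the documents: *c* of 0.80 or 0.90; one-year incidence of 2%, 5% or 10%; everyone at risk with full follow-up.

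| Assumed incidence | Events, either source | GP-only, *c* = 0.90 | GP-only, *c* = 0.80 |
|---|---|---|---|
| 2% | 11,000 × 0.02 = 220 | 198 | 176 |
| 5% | 11,000 × 0.05 = 550 | 495 (4.5%) | 440 (4.0%) |
| 10% | 11,000 × 0.10 = 1,100 | 990 | 880 |

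**Effect of an incomplete history.** If a share *p* of the cohort has prior disease recorded only in hospital, and a share *r* of those receive a GP code in the year, then about *N* × *p* × *r* prevalent cases are counted as new. The documents give neither *p* nor *r*. This error raises apparent incidence, so it partly offsets the first one without correcting it.

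**Effect on the hazard ratio.** Setting the history problem aside, with low incidence and no false-positive codes,

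GP-only HR ≈ either-source HR × *c*₃ / *c*₄,

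where the subscripts are cohorts 3 and 4. Starting from an HR of 1:

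- 0.80 / 0.80 = 1.00
- 0.80 / 0.90 = 0.89
- 0.90 / 0.80 = 1.125

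The sign depends on which cohort has the better capture, and the Protocol has no data on that.

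**Whether existing safeguards close the gap**

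- Cohort 5 shares the calendar period with cohort 3, so a period-wide change in GP coding would affect both. It addresses the calendar cause, but the written model does not include it and it does nothing for objective 4.
- Censoring cohort 4 at 24 January 2020 makes its outcome recording wholly pre-pandemic. It does not bring capture into line with cohort 3.
- The E-value is specified for unmeasured confounding, not for missed outcomes.

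**The case against.** The strongest reply is that one source applied identically to every cohort is a coherent choice. The ICD ranges may only name the disease groups that the Read codes implement, so the two sections need not contradict each other. A hospital diagnosis that the GP enters is still counted. The Data sources sentence is loosely worded: taken literally, it would place the Aim 2 exposures in QResearch, although those are ICU and hospital admissions. Supplemental material S1, which describes the datasets, is not shown, and some coding detail may properly sit in an analysis plan. Adding HES also ties detection to readmission, which may differ between COVID-19 and SARI survivors.

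Most of this stands. It rules out calling the text a proven contradiction, or saying that hospital diagnoses are ignored outright. It also weighs against simply replacing the GP-only outcome with a combined one. It does not explain why linked hospital codes have no part in establishing prior history, or why no analysis shows how much the choice of source matters.

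A reader might go further and infer that GP capture fell in the pandemic, so that the hazard ratio is biased towards fewer COVID-19 sequelae. The documents do not support this. They give no coding completeness for either period. The one period influence on diagnosis that the Bias section names is that COVID-19 patients "may have benefited from the recently increasing public awareness of mental health conditions", which could equally raise recorded diagnoses. Cohort 5 exists to deal with calendar differences. Disorders coded nowhere because patients did not consult could not be recovered from HES, so a general fall in GP recording cannot be put down to leaving HES out.

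**Conclusion.** The point holds as a limit on ascertainment. Followed as written, the plan counts hospital-recorded new disorders only when they reach the GP record and treats hospital-only prior disease as absent. One-year incidence may be under-counted, and some prevalent disease may be labelled new. Under the assumed capture of 80% to 90%, the relative shortfall in recorded incidence is 10% to 20%, before any offset from misclassified prevalent cases. The true figure cannot be derived from the documents.

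Bias in the COVID-19 versus SARI hazard ratio is possible, of unknown size and direction, and roughly nil if capture is equal. The separate ambiguity over which dataset each code list applies to is real but easily settled.

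**What to change.** 1. In the outcome definitions and in Data sources, state for each code list which dataset it is searched in, and say whether the ICD ranges are search codes or only labels for the Read-code groups. Resolve the question mark in the dementia list at the same time.
2. Establish pre-admission history from both QResearch Read codes and HES ICD-10 codes, so that a known disorder is not counted as new.
3. Pre-specify an analysis in which the outcome is the earliest post-discharge code in either source, and report it beside the GP-only definition. State in advance which of the two is primary.
4. Report event counts by source (GP only, HES only, both) and by cohort.
5. Run both definitions for cohort 3 versus cohort 5 as well as cohort 3 versus cohort 4, and write the cohort 5 comparison into the Aim 2 methods.

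The cost is small: further extraction from a dataset that is already linked and already searched for diagnosis codes, plus one repeated set of models. The drawback is that HES ascertainment depends on readmission, so a cohort readmitted more often has more chances to be coded. The two definitions should therefore stand side by side, with the by-source counts showing how far they differ.

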- Cohort four will include adult patients (aged 18+ on date of hospital admission) discharged alive following a hospital admission including an ICU admission resulting from SARI (defined below) admitted between 24 January 2015 and 23rd January 2020, who were registered in a primary care practice within the QResearch programme before their ICU admission. The cohort will allow comparisons to be made with cohort three. Follow-up will be from the date of discharge. Patients will be censored at the earliest of first occurrence of deregistration from the GP practise, death from other causes, 12 months post discharge from hospital or date of the final data extract from the linked datasets.
- Cohort 5 will include adult patients (aged 18+ on date of hospital admission) discharged alive following a hospital admission including an ICU admission resulting from SARI (defined below) between 24 January 2020 and study end date, who were registered in a primary care practice within the QResearch programme before their ICU admission. It will be used to allow comparison with cohort 3. Patients will be censored at the earliest of first occurrence of deregistration from the GP practice, death from other causes, 12

months post discharge from hospital, or date of the final data extract from the linked datasets.

Variables

Definition of outcomes Aim 1

For cohort one, our primary outcome is the first occurrence of any one of the following:

1. Hospital admission resulting from COVID-19 infection defined as testing positive for SARS-CoV-2 (as recorded in the PHE database) in the 14 days prior to or during a hospital admission period in the HES dataset, or having an ICD10 code U07.01 for confirmed COVID-19 diagnosis in that HES admission record

2. Admission to an ICU resulting from COVID-19 infection which will be defined as patients admitted to an ICU within the ICNARC dataset of COVID-19 admissions.

3.All - cause mortality following COVID-19 infection.

Secondary outcomes are each of the three events defined above, considered separately (i.e. COVID-19 hospital admissions; ICU admission; death).

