Royston Parmar flexible parametric survival models will be used to estimate the hazard ratio of severe COVID-19 outcome (hospital or critical care admission and death) in cohort 1 for patients with neuropsychological disease at study entry compared with those without disease, and for individual neuropsychological diseases and treatments.

This analysis will be adjusted for the listed covariates. The age variable will be included as a restricted cubic spline rather than a linear term. Before commencing analysis, we will assess the numbers of patients with each comorbidity, and may if necessary group the presence of certain less common comorbidities together. Any such grouping will be done on the basis of clinical similarities only and prior to examining any outcomes by comorbidity. We may also include a time-varying binary covariate to record any new diagnosis and/or treatment which occurs after study entry in patients originally free from both diagnosis and treatment, depending on the number of these events. Proportional hazards assumptions will be tested, and time dependent terms will be included if the hazard ratio changes over time (I.e. if the association between neuropsychological disease and risk of severe COVID-19 has changed during the course of the pandemic). A random frailty term will be included to account for similarities amongst patients registered in the same primary care practice. Possible interactions between exposure and age, sex and ethnicity will be considered and tested using a Wald test.

The same methods will be used for secondary analyses in which the main exposure variable will be defined as either the presence of a specific class of neuropsychological disorder or any other neuropsychological disorders or no disorder.

The primary analysis will be used to estimate the hazard ratio of severe SARI outcomes in cohort 2 using the same exposure variables.

If non-proportional hazards are observed in either cohorts 1 or 2, then maximum follow-up time will be capped at 1 year and a time-dependent covariate will be added to the analysis of both cohorts to maintain the comparability of results.

Aim 2.

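### The condition-specific analysis offered as the check on differing exposure to COVID-19 models only severe outcomes, so it can show that total associations differ by condition but cannot attribute them to exposure

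*Protocol*

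**What the plan says.** **The bias and its remedy.** The Bias section of the protocol says of Aim 1 that the conditions of cohort 1 patients "are likely to result in varying levels of exposure to covid-19, compared to the populations without these conditions". It expects lower exposure in some conditions and higher in others. The remedy follows directly: "We have added a secondary analysis to examine the effect of specific conditions in order to evaluate this".

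**The analysis named.** Statistical Methods, Aim 1, sets a Royston-Parmar model to "estimate the hazard ratio of severe COVID-19 outcome (hospital or critical care admission and death) in cohort 1". For the condition-specific work, "The same methods will be used for secondary analyses in which the main exposure variable will be defined as either" a specific disorder class, any other disorder, or none. Only the exposure variable changes.

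**The outcomes.** Under Definition of outcomes, Aim 1, the primary outcome for cohort 1 is the first of COVID-19 hospital admission, COVID-19 ICU admission, or death after COVID-19 infection. "Secondary outcomes are each of the three events defined above, considered separately (i.e. COVID-19 hospital admissions; ICU admission; death"). Infection or a positive test is not an outcome in its own right, although the Public Health England RT-PCR registry is linked (Data linkage; Data sources).

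**The population.** To limit testing (collider) bias, "we will analyse the entire QResearch eligible population, rather than restricting analysis to only those with a positive COVID-19 test".

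**Other relevant text.** Sensitivity analyses includes a restriction to patients with RNA-confirmed COVID-19. Quantitative variables plans descriptive summaries by infection status and by presence of neuropsychiatric conditions or treatments.

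**The concern.** A patient has a severe COVID-19 event only by being infected and then becoming severely ill. A model of severe events in everyone, infected or not, measures the two steps together. Dividing the exposure by disorder class gives one combined figure per class and separates the steps in none of them.

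The hazard ratio would track exposure only if severity given infection were the same across conditions. The study hypothesises that prior neuropsychological disease, and particular drug classes, raise the risk of severe outcomes, so that condition cannot be taken for granted.

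What is at stake is interpretation. The protocol names a particular analysis as its check on a particular bias, and a reader who trusts that statement may misread the results in two ways. A condition whose patients are infected more often may be taken as clinically more vulnerable, or as showing a drug effect. A condition in which shielding offsets greater vulnerability may be taken as showing neither.

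**Working it through.** The protocol gives no figure on this point, so there is none to reproduce. The check is whether the named analysis can identify the quantity it is said to evaluate.

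**Step 1. Decomposition.** In a population not conditioned on infection:

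P(severe) = P(infection) × P(severe given infection)

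For a rare outcome the hazard ratio (HR) is therefore about RR_infection × RR_severity. This follows from the outcomes and population in the protocol and needs no assumed rates.

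**Step 2. Illustration.** Assumed, not from the protocol: in the reference group, 10% are infected and 5% of those are severe. Then p0 = 0.10 × 0.05 = 0.005, p1 = p0 × RR_infection × RR_severity, and HR = log(1 − p1) / log(1 − p0).

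| RR_infection | RR_severity | p1 | HR for severe outcome |
|---|---|---|---|
| 0.70 | 1.43 (1/0.70) | 0.0050 | 1.00 |
| 1.00 | 1.40 | 0.0070 | 1.40 |
| 1.40 | 1.00 | 0.0070 | 1.40 |
| 0.70 | 1.00 | 0.0035 | 0.70 |
| 1.00 | 0.70 | 0.0035 | 0.70 |

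Rows 2 and 3 cannot be told apart, nor can rows 4 and 5. In row 1 a 30% lower infection risk leaves no trace. Other assumed baseline risks would change precision but not this pattern, as long as the severe outcome stays rare.

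**Step 3. Does the test-confirmed restriction supply the missing piece?** Assume that all severe cases are tested, that a share t of mild cases is tested, that 5% of infections are severe in both groups (true severity ratio 1.0), and that t = 30% in the reference group. Among test-positive patients the severe share is 0.05 / (0.05 + 0.95t):

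- t = 30%: 0.05 / 0.335 = 0.149
- t = 45%: 0.05 / 0.4775 = 0.105, apparent severity ratio 0.105 / 0.149 = 0.70
- t = 20%: 0.05 / 0.24 = 0.208, apparent severity ratio 0.208 / 0.149 = 1.40

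The restriction separates severity from infection only if testing of mild infection does not differ by condition. The protocol also does not tie it to disorder class or to the exposure question.

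**Step 4. Would a positive-test outcome settle exposure?** Take the 8.3 million adults in Study Size. Assume 8% infected in both groups, 30% of infections detected in the unexposed, a condition prevalence of 1%, and a detection ratio of 1.1.

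- Positive risk: 0.08 × 0.30 = 0.024 in the unexposed, 0.0264 in the exposed.
- Expected positives: 83,000 × 0.0264 = 2,191 and 8,217,000 × 0.024 = 197,208.
- Standard error of the log ratio: √(0.9736/2,191 + 0.976/197,208) = 0.0212.
- z = log(1.1) / 0.0212 = 4.50, so a two-sided 5% test rejects about 99% of the time although infection is equal.

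With a detection ratio of 1.05 the figure is 61%. A positive-test model would therefore respond to small differences in testing, and can only be supportive.

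**The case against.** **The sentence may mean something narrower.** If conditions act in opposite directions, a pooled hazard ratio could hide them, and splitting by class deals with that. This stands as a real benefit of the analysis. However, the sentence follows a statement about exposure to the virus, and what it says will be evaluated is that exposure. Heterogeneity of the total association is a different quantity.

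**The estimand is sound.** Objectives 1 and 2 ask whether diseases and treatments are associated with severe outcomes, and the whole population is analysed deliberately to avoid collider bias. If shielding offsets vulnerability, a ratio near 1 is the correct total association. This stands in full. A reader might infer that the primary analysis is invalid, and the protocol does not support that.

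**No error rate is breached.** A reader might also infer that the analysis has an inflated false-positive rate for exposure. The protocol states no null hypothesis of equal infection and no test of one. Rejecting when severity differs is correct for a severe-outcome hazard ratio.

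**Other parts of the plan bear on infection.** The test-confirmed restriction gives a view of severity among detected cases, and the descriptive summaries set infection status against condition status. Neither is tied to disorder class or to the exposure question. The restriction also brings back the testing bias that the main analysis was designed to avoid.

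**Conclusion.** The point holds as a mismatch between the stated purpose of an analysis and what that analysis can estimate. The condition-specific hazard ratios can show that total associations differ between disorder classes. They cannot show whether a difference comes from exposure or from vulnerability.

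The non-identifiability follows from the protocol's own outcomes and population. The sizes shown (1.40 from either source, 1.00 from ratios of 0.70 and 1.43) rest on assumed infection and severity risks and are illustrations. How far the two components differ by condition in these data is unknown.

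The hazard ratio could serve as a guide to exposure if severity given infection were equal across conditions, so the analysis can mislead but need not. The consequence is confined to how the Aim 1 condition-specific results are explained. It should be corrected before they are interpreted.

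**What to change.** 1. **Reword the Bias section.** State that the condition-specific secondary analysis shows heterogeneity of the total association with severe COVID-19 by condition, and that it does not isolate differences in exposure. This alone removes the contradiction.
2. **Add one supportive secondary analysis.** Model time to first positive RT-PCR result by condition in all of cohort 1, with the same Royston-Parmar model and covariates. Count every positive test wherever it was taken: leaving out tests taken in hospital would make the outcome depend partly on severity. Show the result by pandemic period and by care-home residence, which the domicile covariate already records.
3. **Report the results together.** For each condition, place the positive-test hazard ratio beside the severe-outcome hazard ratio and the test-confirmed sensitivity analysis, the latter also split by condition. State that both test-based results reflect access to testing as well, so that neither alone settles the exposure question.

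The cost is a wording change, one further model per condition on data already linked, and a split of a sensitivity analysis already planned. The downside is that the added result is itself open to testing bias.
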